8.3 Deaths and Serious Adverse Events

Serious adverse events (SAEs) will be listed and summarized in the same manner described in Section 8.2. Separate displays listing and summarizing death, including time to death and cause of death, will also be created.

9. Other Analyses

9.1 Use of Medications

Medications will be coded according to the World Health Organization Drug Dictionary (WHODDE Version 2016.03). Medications reported on the CRF will be categorized for analysis as prior, concomitant, or after study treatment by comparing the medication start and stop dates with the first and last dose of study medication dates. Prior medications will have both the medication start and stop dates prior to the first dose of study medication date. After medications will have both the medication start and stop dates after the last dose of study medication date. All other medications will be classified as concomitant, indicating that use of the medication overlapped with use of the study medication by at least one day.

Displays of concomitant medication data will be limited to asthma and allergy medications for children and adults as well as anti-hypertensives, antipsychotics, antidepressants, and heartburn/GERD medications.

The number and percentage of subjects receiving prior, concomitant, and after medications will be presented overall, by cohort, and by medication class. When reporting the number of subjects receiving the medication, a subject will only be counted once if they ever received the medication within the medication class. Percentages will be based on the number of subjects in the analysis population.

10. Interim Analyses and Data Monitoring

The progress of the study will be monitored by the Data and Safety Monitoring Board (DSMB). The DSMB will be chartered to review safety data and to make recommendations regarding continuation, termination, or modification of the study. The DSMB will formally review the safety data at least yearly. The discontinuation of study treatment will also be periodically reported to the DSMB.

In addition, safety data will be reviewed by the DSMB when an event occurs that is of sufficient concern to the National Institute of Allergy and Infectious Diseases (NIAID) medical monitor or protocol chair to warrant review, or when an event occurs that could contribute to a predefined stopping rule specified in the protocol.

Findings will be reported to Institutional Review Boards (IRBs) and health authorities.

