3.1. Description of Study Design

This is a multi-center, open label pilot study to assess the safety and determine the feasibility of cockroach nasal allergen challenge (NAC) in children with asthma. This pilot study will occur in two phases. Phase 1 will enroll 10 cockroach sensitive adults with asthma who will undergo a nasal allergen challenge with increasing doses of cockroach allergen. This phase will consist of two parts, Phase 1a and Phase 1b. In Phase 1a, the cockroach sensitive adults will undergo the initial NAC. In Phase 1b, the adult participants will undergo a repeat challenge 30-365 days after the Phase 1a NAC. The purpose of Phase 1b is to assess reproducibility of the NAC with cockroach allergen in a population with asthma. Phase 2 will enroll 25 cockroach sensitive children with asthma who will undergo a NAC with increasing doses of cockroach allergen. Progressing to Phase 2 will not be dependent upon the results of Phase 1b, and Phase 2 will proceed immediately after the completion of Phase 1a. After the completion of Phase 1a, the primary outcome data (positive response to NAC, defined as TNSS \geq 8 out of 12 or a sneezing score of 3) for the participants in Phase 1a will be reviewed to determine the optimal dose range to be used in Phase 2. Considerations for choosing the most appropriate dose range will include tolerability and the aim of eliciting a threshold of nasal symptoms. The investigators planned to use the results of the primary outcome analysis (Section 13.4.2) to determine the optimal dose to be used in Phase 2, with the combination of the optimal dose, one dose above, and 2 doses below the optimal dose to be selected as the four doses to be used in Phase 2. However, an optimal dose was not determined in Phase 1a. It was noted that no adult reacted to the first dose of allergen (challenge dose 2).

Phase 2 will enroll 25 cockroach sensitive children with asthma, ages 8-14 years, who will undergo a nasal allergen challenge with all 8 allergen doses used in Phase 1a in at least the first 5 participants to ensure a similar pattern of response. If none of these 5 children react to the first dose of allergen (challenge dose 2), then that dose will be dropped from subsequent challenges. The threshold for a positive response to the NAC in Phase 2 will be defined as a TNSS \geq 6; the sneezing score of 3 will remain the same.

[figure not shown]

Figure 3.1 Cockroach Nasal Allergen Challenge Study Design

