7.4. Rescue Medications

Participants may use antihistamines and/or a nasal steroid as needed for persistent nasal and/or ocular symptoms following the nasal allergen challenge. If at any time during the nasal challenge a participant experiences asthma symptoms or anaphylaxis, treatment with inhaled short-acting bronchodilators, corticosteroids and epinephrine will be immediately available. Participants will be instructed to bring an albuterol inhaler to any Challenge Visit and carry it with them for the first 24 hours after the challenge. Participants who do not bring an albuterol inhaler to a Challenge Visit will be provided one.

8. Study Procedures

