11. Nasal allergen challenge (NAC) - increasing doses of allergen in defined time intervals (every 20 minutes) up to a specified maximum dose or symptom level, will be given as described in an accompanying MOP for Protocol ICAC-27. Briefly, one spray (100mcL) of diluent or diluted allergen solution is applied to each of the participant's nostrils using a nasal drug delivery system while the participant breath-holds at TLC. After the dose is delivered, the participant is asked to exhale through the nose and then to avoid sniffing or swallowing in the immediate 1 minute after application. In Phase 1, the challenge will begin with a 0 mcg/ml (negative control – 50% glycerin, 50% COCAS with 0.2% phenol) dose followed by up to 8 doses of increasing concentration, until the participant reaches a TNSS score of 8 or more, has a sneezing score of 3 or their symptoms become intolerable. In Phase 2, the challenge will begin with a 0mcg/ml (diluent control) dose followed by a number of doses of increasing concentration, until the participant reaches a TNSS score of ≥ 6 , has a sneezing score of 3 or their symptoms become intolerable. All 8 allergen doses will be used in the first 5 children in Phase 2 to ensure a similar response pattern to that seen in the adults. If, like in Phase 1 in adults, none of these 5 children react to the first allergen dose, this dose will be dropped from the subsequent challenges. Nasal secretions will be collected for approximately 10 minutes immediately following administration of each diluent and allergen dose and a nasal rinse (two 100mcL sprays of isotonic saline solution per nostril) will be performed at 10 minutes, as described above. The fluids from each rinse will be mixed with the nasal secretions collected during the preceding 10 minutes and processed for analysis as specified in the MOP for Protocol ICAC-27. Collection of other outcomes will begin 10 minutes after each diluent or allergen dose is administered. If a participant begins exhibiting asthma symptoms during the NAC, or the PEF is reduced by more than 20% from baseline, the challenge will be suspended, and the participant will be evaluated by the study clinician. If it is determined treatment is needed based on clinical judgment, then the challenge will not be continued. In the absence of an immediate need for treatment, spirometry will be performed to confirm a change in lung function. If the FEV1 is $< 85\%$ of baseline value, the challenge will be stopped. If spirometry is performed because of a low PEF and the FEV1 is $\geq 85\%$ of baseline value, the challenge can continue at the clinician's discretion.

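### SAP 9.1 labels every medication taken wholly between an adult's two challenges as overlapping study drug, so its tables are not comparable across cohorts and cannot isolate post-challenge use

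*SAP*

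**What the plan says.** SAP 9.1 classifies each medication "by comparing the medication start and stop dates with the first and last dose of study medication dates". The two outer classes are explicit: "Prior medications will have both the medication start and stop dates prior to the first dose of study medication date", and "After medications will have both the medication start and stop dates after the last dose of study medication date". Every other medication is concomitant, a label the SAP explains as "indicating that use of the medication overlapped with use of the study medication by at least one day". Counts are shown overall, by cohort and by medication class. SAP section 4 names two cohorts, Phase 1 adults and Phase 2 children. SAP 9.1 has no split by challenge and no rescue category.

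On exposure, Protocol 3.1 states: "In Phase 1b, the adult participants will undergo a repeat challenge 30-365 days after the Phase 1a NAC". Protocol 8.3 describes each challenge as "increasing doses of allergen in defined time intervals (every 20 minutes) up to a specified maximum dose or symptom level", all within one visit. Phase 2 children have one challenge.

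On medication around the challenge, Protocol 7.4 foresees rescue: "Participants may use antihistamines and/or a nasal steroid as needed for persistent nasal and/or ocular symptoms following the nasal allergen challenge". Protocol 7.1.2 permits rhinitis, asthma and maintenance medication after the initial skin testing. Protocol 7.3 requires antihistamines and nasal treatments to be suspended before any Challenge Visit.

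**The concern.** The rule suits a drug given continuously, where the period from first to last dose is the exposure period. Here exposure is one day, or two days far apart, and the interval between the two challenges is almost entirely unexposed. For courses inside that interval, the SAP's explanation of the label is untrue.

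Two things are at stake, both in the descriptive tables.

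- **Meaning of concomitant in adults.** An adult who takes an antihistamine between challenges and stops it in time for washout is tabulated as having used it during study medication. The table cannot distinguish that from use on a challenge day.
- **Comparability.** The label given to the same behaviour depends on whether the adult came back. Returning is linked to tolerability, because Protocol 4.2 admits to Phase 1b only adults with no local-reaction adverse event of grade 2 or higher in Phase 1a. Post-challenge use is therefore labelled differently in adults who tolerated the challenge, adults who did not, and children.

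**Working it through.** The plan gives no figure to reproduce. The check applies the rule literally, with one first and one last dose date per participant.

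**Inputs**

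- Gap G between an adult's challenges: 30 to 365 days (Protocol 3.1).
- Dosing days: 2 for an adult with both challenges, 1 otherwise (Protocol 8.3).
- Day 0 is the Phase 1a (or only) challenge; day G is the Phase 1b challenge.
- Rule (SAP 9.1): *prior* if start and stop are both before day 0; *after* if both follow the last dose date; otherwise *concomitant*.

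**Step 1. Length of the interval.** Days strictly between the challenges number G − 1, which is 30 − 1 = 29 to 365 − 1 = 364. The span from first to last dose covers G + 1 calendar days, of which 2 are dosing days: 2/31 = 6.5% at the shortest gap and 2/366 = 0.5% at the longest.

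**Step 2. Courses wholly between the challenges.** With n = G − 1 days available, the number of possible start/stop pairs is n(n + 1)/2.

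- G = 30: 29 × 30 / 2 = 435.
- G = 365: 364 × 365 / 2 = 66,430.

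None starts before day 0 or ends after day G, so all 435 and all 66,430 are labelled concomitant. None includes day 0 or day G, so the true overlap is zero in every case, against the stated minimum of one day. These are counts of possible courses, not estimates of how many will occur.

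**Step 3. The same use under different participation**

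| Course | Adult with both challenges | Adult with 1a only, or child | Dosing days overlapped |
|---|---|---|---|
| Days 1–3 after the first or only challenge | concomitant | after | 0 |
| Days 10–12 after the first or only challenge | concomitant | after | 0 |
| Challenge day only | concomitant | concomitant | 1 |
| Ongoing throughout | concomitant | concomitant | 2 or 1 |
| Days 1–3 after the Phase 1b challenge | after | not applicable | 0 |

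Rows 1 and 5 show that, in the same returning adult, identical use gets different labels after the two challenges.

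**Step 4. Effect of using each challenge as its own reference.** The days 1–3 course becomes *after* for Phase 1a and *prior* for Phase 1b, which is correct. The days 10–12 course gets the same pair of labels, so per-challenge dates alone do not separate early post-challenge use from later use. A course on the challenge day stays concomitant, because the rule compares dates and not times.

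**The case against.** A reader might infer that rescue use after the first challenge cannot be seen anywhere in the analysis. The documents do not support that. Protocol Table 12.3.1a makes a local reaction to the challenge that needs antihistamines, decongestants or nasal steroids a grade 1 adverse event, and one that needs oral steroids grade 2. Protocol 12.3.2 confirms that events reaching those levels are recorded and reported. SAP 8.1 analyses adverse events separately for Phases 1a, 1b and 2, and SAP 8.2 reports maximum severity on each applicable scale. Concomitant medications are also assessed the day after the challenge and at the 6–10 day contact (Protocol 8.5 and 8.6). This part of the objection stands. Its limit is that the adverse event tables are organised by system organ class, preferred term and severity rather than by drug, and SAP 9.1 promises no medication listing.

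It can also be said that only returning adults are affected, and their Phase 1a local reactions were grade 1 at most. That is right. Phase 1b can also be refused (Protocol 11.1), so 10 is a ceiling.

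A per-challenge reading of first and last dose is possible: the SAP refers elsewhere to a Phase 1a cohort and analyses safety by phase. SAP 9.1 does not say so, however, and it tabulates by cohort where section 4 defines a single Phase 1 adult cohort. If per-challenge dates are intended, one sentence would settle it.

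Finally, counting every allergy or asthma drug started after a challenge as rescue would be a new error, since it would include usual treatment resumed after washout. That stands, and the fix allows for it.

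**Conclusion.** The point holds as a defect in the SAP 9.1 medication tables. On the participant-level reading, every course lying wholly between an adult's two challenges is called concomitant with an overlap that does not exist. Post-challenge use is labelled inconsistently between returning adults on the one hand and non-returning adults and children on the other.

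At most 10 adults are affected, each with 29 to 364 days of interval. How many medications will be mislabelled cannot be derived from the documents. The conclusion assumes that first and last dose dates are taken per participant across Phases 1a and 1b.

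Materiality is low. The response analysis and the adverse event counts do not use this classification. The documents support saying that the medication tables cannot isolate post-challenge use; they do not support saying that such use is lost to the study.

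**What to change.** In SAP 9.1:

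1. Define prior, concomitant and after relative to each challenge date separately (1a, 1b, 2), and tabulate by challenge. One course may then be *after* for Phase 1a and *prior* for Phase 1b, so the challenge-specific counts should not be added together.
2. Correct the overlap statement so that concomitant means use on the challenge date in question.
3. For each challenge, add a *started post-challenge* row for asthma and allergy medications begun from the challenge through the 6–10 day contact. Challenge-day starts need a start time or a flag to show that they followed dosing.
4. Call use *rescue* only where the recorded indication or a linked adverse event supports it.

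The cost is SAP wording, one date derivation per challenge and a changed layout for descriptive tables. Steps 1 and 2 need only medication and challenge dates. Steps 3 and 4 assume that the case report form holds an indication, an adverse event link, or a start time or flag for challenge-day use. The documents do not say whether it does; where it does not, the row should be reported without the rescue label.
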